10.7 Analysis of the secondary efficacy variables

Secondary efficacy variables will be analyzed for the PPS at $\alpha = 0.05$ (two-sided) using 95% CIs. Additionally, change from baseline to Week 8 in mean trough SiSBP will be analyzed for the FAS. No correction for multiple testing will be applied for these analyses.

Change from baseline to Week 8 of DB treatment period (Period II) in mean trough SiSBP will be analyzed similarly to the primary endpoint (SiDBP), i.e., MCP-Mod will be applied, supplemented by the ANCOVA and the repeated measurements models described above. The correlation between the changes from baseline in SiDBP and SiSBP will be displayed in a scatter plot for each post-baseline time point.

Control (< 90 mmHg and < 85 mmHg, separately) and response (Y/N) at Week 8 of DB treatment period (Period II) based on trough SiDBP will be analyzed using a logistic regression model with a factor for treatment group and a covariate for baseline mean trough SiDBP. Control and response status at Week 8 of Period II based on trough SiSBP will be analyzed similarly.

Change from baseline to Week 8 of DB treatment period (Period II) in 24-hour mean DBP based on ABPM will be analyzed using an ANCOVA with a factor for treatment group and a covariate for baseline 24-hour mean DBP. Change from baseline to Week 8 of DB treatment period (Period II) in 24-hour mean SBP based on ABPM will be analyzed similarly.

The baseline and Week 8 average ABPM-DBP curves over time (by hour) will be plotted by treatment group [averaging as described in Section 5.5.2]. Additionally, the Week 8 minus baseline difference will be plotted vs time. Trough to peak ratios for DBP will be calculated by treatment group as described in Section 5.5.2.

10.8 Analysis of other efficacy variables

Other efficacy analyses will be performed on the PPS.

Changes from baseline to Week 2 (time window Visit 5) and Week 4 (time window Visit 6) of DB treatment period (Period II) in mean trough SiSBP and SiDBP (OBPM) will be obtained from the repeated measurements model as described in Section 10.6.4 under *sensitivity analysis*.

Change from baseline to Week 8 of DB treatment period (Period II) in mean daytime DBP (SBP) measured by ABPM will be analyzed using an ANCOVA with a factor for treatment group and a covariate for baseline mean daytime ABPM. Change from baseline to Week 8 of DB treatment period (Period II) in mean night time DBP (SBP) measured by ABPM will be analyzed similarly.

ABPM-SBP curves will be plotted and trough to peak ratios for SBP will be calculated as described for DBP based on ABPM.

Changes from baseline to Week 10 (time window Visit 8; Week 2 of withdrawal period - Period III) in mean trough SiSBP and SiDBP (OBPM) will be obtained by extending the repeated measurements model described in Section 10.6.4 with an additional time point for time window Visit 8 (Week 10 i.e., Week 2 of withdrawal period - Period III).

Changes from Week 8 of Period II to time Week 10 (time window Visit 8; Week 2 of withdrawal period - Period III) in mean trough SiSBP and SiDBP (OBPM) will be obtained from the same model using appropriate treatment and time contrasts.

All efficacy analyses are summarized in [Table 4](#).

Table 4 Summary of efficacy analyses

Efficacy analysis	Endpoint	Measure	Week	Model	Dataset(imputation)	
Primary	SiDBP	OBPM	8	MCP-Mod	PPS	
- Supportive	SiDBP	OBPM	8	MCP-Mod		FAS (LOCF)
	SiDBP	OBPM	8	ANCOVA (Dunnett)	PPS	FAS (LOCF)
- Sensitivity	SiDBP	OBPM	8	MCP-Mod		FAS (BOCF)
	SiDBP	OBPM	8	MCP-Mod based on mixed model ^a		FAS (OC)
- Average over time	SiDBP	OBPM	2,4,8	MCP-Mod based on mixed model ^b	PPS	FAS (OC)
- Subgroup	SiDBP	OBPM	8	MCP-Mod by subgroup	PPS	
Secondary	SiSBP	OBPM	8	MCP-Mod	PPS	FAS (LOCF)
	SiSBP	OBPM	8	ANCOVA (Dunnett)	PPS	FAS (LOCF)
	SiSBP	OBPM	8	MCP-Mod based on mixed model ^a		FAS (OC)
	Average SiSBP over time	OBPM	2,4,8	MCP-Mod based on mixed model ^b	PPS	FAS (OC)
	Subgroup SiSBP	OBPM	8	MCP-Mod	PPS	
	Control/ response of SiDBP	OBPM	8	MCP-Mod based on logistic regression	PPS	
	Control/ response of SiSBP	OBPM	8	MCP-Mod based on logistic regression	PPS	
	24-hour mean DBP	ABPM	8	ANCOVA	PPS ^c	
	24-hour mean SBP	ABPM	8	ANCOVA	PPS ^c	
	Trough to peak ratio DBP	ABPM	8	Descriptive statistics	PPS ^c	
Other	Mean daytime DBP	ABPM	8	ANCOVA	PPS ^c	

Efficacy analysis	Endpoint	Measure	Week	Model	Dataset(imputation)	
	Mean night time DBP	ABPM	8	ANCOVA	PPS ^c	
	Mean daytime SBP	ABPM	8	ANCOVA	PPS ^c	
	Mean night time SBP	ABPM	8	ANCOVA	PPS ^c	
	Trough to peak ratio SBP	ABPM	8	Descriptive statistics	PPS ^c	
	SiDBP	OBPM	8,10	ANCOVA	PPS	
	SiSBP	OBPM	8,10	ANCOVA	PPS	

* If applicable. In the PPS all analyses are based on OC.

^a Also including Week 2 and 4 data, but only to predict missing Week 8 data.

^b Including Week 2, 4 and 8 data to estimate the average effect of time.

^c ABPM analyses are based on the subset of the PPS described in Section 5.5.

ABPM = ambulatory blood pressure monitoring; ANCOVA = analysis of covariance; BOCF = baseline observation carried forward; DBP = diastolic blood pressure; FAS = Full Analysis Set; LOCF = last observation carried forward; MCP-Mod = Multiple Comparison Procedure – Modeling; OBPM = automated office blood pressure measurement; OC = observed cases; PPS = Per-Protocol Set; SBP = systolic blood pressure; SiDBP = sitting diastolic blood pressure; SiSBP = sitting systolic blood pressure.

MCP-Mod based on mixed model (logistic regression, ANCOVA) implies that first the mixed model (logistic regression, ANCOVA) is performed and then the estimated differences vs placebo are analyzed using the general MCP-Mod approach [Pinheiro 2014].

10.9 Analysis of safety variables

All safety analyses described below will be performed on the SAF. All safety data will be listed, with flags for abnormalities, when applicable.

10.9.1 Adverse events

All reported AEs will be listed, together with the assigned preferred term/SOC. The listings will indicate the period of onset of the AE (run-in, DB treatment or placebo WD).

Treatment-emergent AEs [see definition in Section 5.6.1.1] will be summarized displaying, for each treatment group, counts and percentages of subjects having experienced at least one treatment-emergent AE. Counts and percentages of subjects having experienced at least one treatment-emergent AE are presented by SOC and individual preferred term within each SOC. The summary tables are presented in descending order according to the incidence in the highest-dose of active test treatment (e.g., SOC and individual preferred term within each SOC with the highest number of

occurrences appears first). Equal frequency of different SOC/individual preferred terms is sorted in alphabetical order of the SOC/individual preferred term.

Treatment-emergent AEs related to study treatment, treatment-emergent AEs leading to premature discontinuation of study treatment and treatment-emergent AEs with fatal outcome will be summarized, separately, by SOC and individual preferred term.

Treatment-emergent AEs, treatment-emergent AEs leading to premature discontinuation of study treatment and treatment-emergent AEs with fatal outcome will be summarized also by preferred term only. Treatment-emergent AEs are also summarized by maximum intensity.

For the disclosure of the results to EudraCT and ClinicalTrials.gov (rather than for the purpose of the clinical study report), a summary table with an overview of treatment-emergent AEs is provided displaying, for each treatment group, counts and percentages of subjects having experienced at least a treatment-emergent AE, a severe AE, a study-treatment related AE, an AE leading to study treatment discontinuation, a non-serious frequent AE, a serious AE, a study-treatment related serious AE, a fatal SAE.

The occurrence of non-serious, frequent (i.e., the percentage of subjects in at least one of the treatment groups equals or exceeds five percent) treatment-emergent AEs will be tabulated by SOC and individual preferred term within each SOC.

10.9.2 Deaths, other serious adverse events

10.9.2.1 Deaths

The primary cause of death coded according to MedDRA dictionary [see Section 5.6.2] will be summarized displaying, for each treatment group, counts and percentages of subjects by class and individual preferred term within each class; the summary table is presented in descending order according to the incidence in the highest-dose of active test treatment (equal frequencies are sorted in alphabetical order).

All deaths will be listed. The listings will indicate the period in which the death occurred (run-in, DB treatment, placebo WD).

10.9.2.2 Serious adverse events

All reported SAEs will be listed and tabulated as described above for AEs.

The occurrence of treatment-emergent serious AEs will be summarized by SOC and individual preferred term within each SOC. The table is presented in descending order according to the incidence in the highest-dose of active test treatment (i.e., SOC and individual preferred term within each SOC with the highest number of occurrences appears first). Ties are sorted in alphabetical order.

Treatment-emergent SAEs will also be summarized by preferred term only.

For the disclosure of the results to EudraCT and ClinicalTrials.gov (rather than for the purpose of the clinical study report), treatment-emergent SAEs will be summarized displaying, for each treatment group, counts and percentages of subjects with at least a treatment-emergent SAE plus the number of events (counted exactly the number of times they occurred also within a subject) by SOC and individual preferred term. The summary table is presented in descending order according to the incidence in the highest-dose of active test treatment (i.e., SOC and individual preferred term within each SOC with the highest number of occurrences appears first). Equal frequency of different individual preferred terms is sorted in alphabetical order of the individual preferred term. Similarly, a separate summary is presented for treatment-emergent SAEs related to study treatment. In addition, treatment-emergent SAEs with fatal outcome and treatment-emergent SAEs with fatal outcome related to study treatment will be summarized separately, similarly to treatment-emergent SAEs.

10.9.2.3 Adverse events leading to study treatment discontinuations

A separate subject listing is provided with treatment-emergent AEs leading to study treatment discontinuation. Treatment-emergent AEs leading to premature study treatment discontinuation will be summarized by SOC and preferred term as well as by preferred term only.

10.9.2.4 Other adverse events

Not applicable.

10.9.3 Electrocardiography (ECG)

Double-blind treatment-emergent ECG abnormalities [see definition in Section 5.6.7.1] will be summarized, by treatment group, displaying counts and percentages of subjects (and 95% confidence limits according to the Clopper-Pearson method) with at least one treatment-emergent ECG abnormality. Values from unscheduled visits are included. Subjects may be included in more than one category as the marked abnormality are presented cumulatively.

ECG variables are displayed in a subject listing on the SCR set; a separate listing is provided of all ECG variables, restricted to subjects with at least one abnormality [see Section 5.6.7 for details].

10.9.4 Laboratory tests

All hematology and chemistry parameters provided by the central and local laboratory are displayed in a subject listing. Marked laboratory abnormalities will be flagged

accordingly. Laboratory values below the limit of detection (i.e., preceded by '<') will be replaced by half that limit in calculations as well as in determining abnormalities.

Hematology, chemistry and urine parameters UACR will be summarized by treatment group for each time window visit. Changes from baseline in these parameters will be summarized for each post-baseline assessment, displaying:

- observed values at baseline and at the post-baseline visit window
- absolute change from baseline to post-baseline visit window

In each evaluation only subjects who had both the assessments at baseline and the considered post-baseline time point are included.

10.9.4.1 Treatment-emergent marked laboratory abnormalities

For each category (i.e., LL, LLL, HH, HHH, HHHH), treatment-emergent marked laboratory abnormalities [see definition in Section 5.6.8.1] will be summarized by treatment group, displaying counts and percentages of subjects with at least a treatment-emergent marked laboratory abnormality for each parameter for which the marked abnormality is defined. Values from unscheduled visits are included. Subjects may be included in more than one category for the same parameter.

In addition, the number of patients with $ALT > 3 \times$ upper limit of normal (ULN) and bilirubin $> 2 \times$ ULN will be tabulated by treatment group and time point (baseline, Week 8).

Percentages are calculated as number of subjects with at least one abnormality for the parameter under consideration divided by the number of subjects with any post-baseline laboratory measurement.

The distribution of the changes from baseline in hemoglobin will be plotted for each post-baseline visit. As an exploratory analysis, dose trends in the change from baseline to Week 8 in hemoglobin will be analyzed using the MCP-Mod approach. The active comparator will be excluded from these analyses.

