5.1.12 Study-specific criteria for interruption / premature discontinuation of study treatment

A) Hypertension

At any time throughout the study if mean SiDBP \geq 110 mmHg and/or mean SiSBP \geq 180 mmHg is measured by OBPM, i.e., essential hypertension grade 3 [Mancia 2013], BP must be re-measured. If the value (i.e., mean SiSBP \geq and/or DBP \geq 110 mmHg measured by OBPM at the site) is confirmed, subject must permanently discontinue study treatment.

The BP re-measurement can be during the same visit (e.g., within 1 h), or at the next planned visit, or at an unscheduled visit. The time of re-measurement is at investigator's discretion, taking into consideration the subject's medical history.

B) Pregnancy

If a female subject becomes pregnant while on study treatment, study treatment must be discontinued immediately, and a Pregnancy Form must be completed [see Section 10.3].

C) Liver aminotransferases abnormalities

Interruption of study treatment

After randomization study treatment must be interrupted in the following cases:

• Aminotransferases (i.e., ALT and/or AST) ≥ 3 and $\leq 8 \times ULN$

Perform a re-test of aminotransferases (ALT and AST), total and direct bilirubin, and alkaline phosphatase within 48 h. If AST and/or ALT elevation is confirmed, the re-introduction of study treatment is not to be considered.

Interruptions must be for less than 5 consecutive days; longer interruptions must lead to permanent discontinuation of study treatment [see Section 5.1.10].

Aminotransferases, total and direct bilirubin, and alkaline phosphatase levels must be monitored weekly after study drug discontinuation until values return to pre-treatment levels or within normal ranges.

Permanent discontinuation of study treatment

Study treatment must be stopped and its re-introduction is not to be considered in the following cases:

- Aminotransferases > 8 × ULN.
- Aminotransferases ≥ 3 × ULN and associated clinical symptoms of liver injury, e.g., nausea, vomiting, fever, abdominal pain, jaundice, unusual lethargy or fatigue, flu like syndrome (arthralgia, myalgia, fever).

Essential hypertension Protocol AC-080A201 Version 3 30 May 2016, page 51/112

Confidential

• Aminotransferases $\geq 3 \times \text{ULN}$ and associated increase in total bilirubin $\geq 2 \times \text{ULN}$.

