7.3.5.2 Laboratory tests

The total amount of blood collected during the study is provided in the laboratory manual. This is approximately 96 mL (10 mL for hematology / clinical chemistry including pregnancy test [if applicable], 8 mL for PK and pharmacodynamic [PD] samples, and 2 mL for pregnancy test at follow-up visit):

- At Visit 1: One sample, only if no historical (within 3 months to this visit) laboratory data available;
- At Visits 3 and 4: One sample;

^{*} Except historical local laboratory data of Visit 1.

Essential hypertension Protocol AC-080A201 Version 3 30 May 2016, page 62/112

Confidential

• At Visits 5, 6, and 7: Two samples; one for the hematology / clinical chemistry / pregnancy analysis, and one for PK and PD analysis); and

- At Visit 8: One sample.
- Follow-up visit, only for women of childbearing potential: One sample for serum pregnancy test.

Hematology

- Hemoglobin, hematocrit
- Erythrocyte count
- · Leukocyte count with differential counts
- Platelet count.

Clinical chemistry

- Aminotransferases (AST/ALT), alkaline phosphatase, total and direct bilirubin, LDH
- Creatinine, creatinine clearance
- Uric acid
- Glucose
- Sodium, potassium
- Protein, albumin
- Free T3, free T4, thyroid stimulating hormone (TSH).

Urinalysis

At Visits 4, 5, 6, 7 and 8 a midstream, clean-catch urine specimen (about 10 mL) will be collected for dipstick analysis and determination of UACR.

UACR determination:

The collected urine will be transferred into a standard urine collection tube for shipment to central laboratory. Details about the collection, sampling, storage, shipment procedures, transfer and reporting of results can be found in the laboratory manual.

Dipstick analysis:

- Bilirubin, urobilinogen
- Blood
- Glucose
- Ketone
- Leukocytes
- Nitrite

Essential hypertension Protocol AC-080A201 Version 3 30 May 2016, page 63/112

Confidential

- pH
- Protein.

Urine dipsticks provided by the central laboratory will be used to perform the urinalysis. The test should be performed and analyzed at the site. The results must be documented in the source documents / subject charts. No data will be collected in the eCRF. Clinically relevant findings meeting the definition of an AE (new AE, or worsening of previously existing condition) [see Section 10.1] will be recorded accordingly on the AE page of the eCRF.

Pregnancy test

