8.4 Premature End-of-Treatment visit (Visit 9)

All subjects who prematurely discontinue study treatment must have Visit 9 performed as soon as possible but not longer than 7 days after the last dose of study treatment, provided that the subject's consent for this limited participation in the study has not been withdrawn.

Essential hypertension Protocol AC-080A201 Version 3 30 May 2016, page 74/112

Confidential

The following assessments are to be performed at premature EOT / Visit 9:

- Sitting BP and HR, and standing BP, measured by OBPM device.
- Physical examination and body weight.
- *12-lead ECG.
- *Laboratory test (i.e., hematology, blood chemistry, and pregnancy test if applicable).
- *Urinalysis (dipstick by site / UACR by central laboratory).
- Reporting of AEs and SAEs.
- Recording of changes in concomitant medications.
- *Assessment of childbearing potential and recording of changes in contraception methods.
- Check compliance with study treatment.
- Retrieve study treatment bottles.
- Make an appointment for the follow-up telephone call or, *for women of childbearing potential, an appointment for the follow-up visit.
- * If subject discontinued study treatment during run-in period,
- This test may not be performed, and
- For women of childbearing potential, a follow-up telephone call can be made instead of the follow-up visit.

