Baseline for laboratory data is defined in Section 5. Each condition is triggered at any post-baseline time point of measurement up to the double-blind treatment end date plus 30 days (included). When determining double-blind treatment-emergent marked laboratory abnormalities, all assessments (including the unscheduled ones) are considered.

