11 GENERAL DEFINITIONS AND DERIVATIONS

11.1 Time windows

To allow analysis of data at the relevant planned (scheduled) visits, all recorded assessments, including unscheduled ones, are re-assigned to the most appropriate visit according to the best fitting time window for that visit [see Table 5]. Note that there are no 'gaps' between the visit windows in order to keep all values in the analysis.

Table 5 Visit time windows

Visit	Target day*	Min. day	Max. day
1	-42	-	-35
2	-28	-34	-18
3	-7	-17	-4
4	1	-3	1
5	14	1	21
6	28	22	42
7 - I	55	43	EOT***
7 - II**	56	EOT + 01 m	EOT + 25 h
8	70	EOT + 25 h 01 m	No limit

* Number of days from start of double-blind treatment.

** Only for ABPM.

*** For OBPM use EOT + 05 m (for the time of the average SiDBP)

ABPM = ambulatory blood pressure monitoring; EOT = End-of-Treatment; OBPM = office blood pressure measurement; SiDBP = sitting diastolic blood pressure.

For assessments for which time is collected, please use the following rules:

- Target day = Target day and time 12:00
- Min. day = Min. day and time 0:00
- Max. day = Max. day and time 23:59

Visit 4 / Day 1

- Target day 1 = Start date/time of DB treatment
- Max. day1 = Start date/time of DB treatment

Visit 5 / Day 1

- Min. day 1 = Start date/time of DB treatment + 1 minute

Visit 7 - I / EOT

- Max. day = End date/time of DB treatment

Visit 7 - II / EOT

- Min. day = End date/time of DB treatment + 1 minute

In the event that there is more than one value within the same time window, the value closest to the planned assessment date will be taken. In the event of equidistant values from the planned time point, the last assessment will be considered for the analyses. Where multiple assessments fall on the same day the latest is then used.

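### The only by-arm table of joint ALT and bilirubin elevation looks at baseline and Week 8, so it misses cases that stop treatment before Day 43 or arise after the last dose

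*SAP*

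**What the plan says.** SAP 10.9.4.1 adds a table of patients with ALT above 3×ULN and bilirubin above 2×ULN, which "will be tabulated by treatment group and time point (baseline, Week 8"). It is output CHE_ALT_BIL in SAP 13.11, on the Safety Set, and is the only joint ALT/bilirubin output listed.

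SAP 5.6 assigns safety assessments to time-window visits and equates Week 8 with Visit 7. In Table 5 of SAP 11.1 the Visit 7-I window starts on Day 43 and ends at end of treatment: "Max. day = End date/time of DB treatment". The five-minute extension beyond that point is for office blood pressure only, and window 7-II is for ambulatory monitoring only.

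Protocol 5.1.12, part C, states: "Study treatment must be stopped and its re-introduction is not to be considered in the following cases". One of the listed cases is aminotransferases of at least 3×ULN "and associated increase in total bilirubin" to at least 2×ULN.

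For single-parameter marked abnormalities, SAP 5.6.8.1 uses a wider rule: "Each condition is triggered at any post-baseline time point of measurement up to the double-blind treatment end date plus 30 days (included"). Unscheduled values are included.

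**The concern.** The table uses a fixed visit for an event that, by protocol, takes the subject off treatment. Subjects with an early joint elevation stop, and stopping removes them from the visit at which the table looks. The other column offers little, because ALT or AST above 3×ULN at screening or Visit 3 is an exclusion criterion, so few baseline cases are expected.

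At stake is how the table reads. This trial has a joint liver stopping rule, a joint laboratory alert and an independent liver board. A reader would take a row of zeros by arm as evidence that no such case occurred, and the specification does not support that reading. The section also does not say whether both elevations must come from the same sample.

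**Working it through.** No figure in the plan needs reproducing. The check applies the SAP's visit windows to the cases the table is meant to show.

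**Inputs**
- Week 8 window for laboratory data: Day 43 to end of double-blind treatment (EOT), target Day 55 (SAP 11.1, Table 5).
- Earlier windows: Visit 5 ends on Day 21; Visit 6 covers Days 22–42 (same table).
- Visit 7 Part 1, with the last double-blind dose: Day 55 ± 5 (Protocol 8.2.4.1).
- Scheduled post-baseline chemistry: "At Visits 5, 6, and 7: Two samples; one for the hematology / clinical chemistry / pregnancy analysis", plus one sample at Visit 8 (Protocol 7.3.5.2). Target days are 14, 28, 55 and 70.
- Premature EOT visit: "not longer than 7 days after the last dose of study treatment" (Protocol 8.4). Liver tests continue weekly after a liver-related stop (Protocol 5.1.12).
- Single-parameter window: to EOT + 30 days (SAP 5.6.8.1).

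**Early case.** As an illustration, suppose the criterion is met at the Day 28 visit and the last dose is on Day 30. The qualifying sample belongs to Visit 6. The Week 8 window would have to run from Day 43 to Day 30, so it is empty. The premature EOT visit and the weekly liver tests come after EOT and are outside it too. The same holds for any EOT before Day 43, because the minimum day then exceeds the maximum.

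**Late case.** A sample first positive after the last dose (premature EOT visit, weekly liver test or Week 10) is past the window's upper limit. For EOT on any of Days 2–60 and a sample 1–30 days later, none falls in Week 8.

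**Boundary.** The enumeration took onset on Days 2–42, stopping 0–5 days later, a re-test two days after onset and weekly samples after the stop. The only countable subjects were positive on Day 41 or 42, were still on treatment on Day 43 or later (EOT Days 43–47), and were re-tested inside the window. They did not stop before Day 43.

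**Coverage**

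| Quantity | EOT Day 50 | EOT Day 55 | EOT Day 60 |
|---|---|---|---|
| Week 8 window, EOT − 43 + 1 (days) | 8 | 13 | 18 |
| Treatment days before it, 42/EOT | 42/50 = 84% | 42/55 = 76% | 42/60 = 70% |
| Window to EOT + 30 (days) | 80 | 85 | 90 |
| Share covered by Week 8 | 8/80 = 10% | 13/85 = 15% | 18/90 = 20% |

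Of the four scheduled chemistry samples, only Visit 7 is in the Week 8 window. Visit 8 at its latest (Day 73) is still before the earliest EOT + 30 (Day 80), so the SAP 5.6.8.1 rule would take in all four.

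**Two further points.** When several values fall in one window, SAP 11.1 keeps the one nearest the planned day, so a positive value between Day 43 and EOT can be displaced by a later normal one. And if the section's percentage rule applies to this table, with the count "divided by the number of subjects with any post-baseline laboratory measurement", an early case stays in the denominator but cannot enter the Week 8 numerator.

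**The case against.** The strongest reply is that no case is lost to the trial. The liver board assesses hepatic events as they arise. The central laboratory raises alerts on these values. Aminotransferase abnormalities that lead to interruption or discontinuation must be recorded as adverse events, and adverse events leading to discontinuation are tabulated. The laboratory listing flags marked abnormalities, includes unscheduled values and is sorted by randomized treatment, so a reader could tally joint cases by arm. The table itself is a descriptive addition in the SAP, is not marked as a key output, and feeds no test or stopping rule.

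All of this is correct, and it limits the severity. It does not supply a by-arm joint count. Separate ALT and bilirubin tables do not show whether the same subject had both, and a hand tally from a listing is not a planned summary.

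Some narrower points also stand:
- The percentage rule is worded for single parameters, so the denominator remark is only conditional.
- Using one value per window already places both elevations in the same visit window, though not necessarily in the same sample.
- The scheduled follow-up draw is a pregnancy test only. Chemistry after Week 10 would come from post-stop liver monitoring or unscheduled tests.
- SAP 11.6 sets a missing end time to 23:59 when it is not taken from the ambulatory recording, and imputes a missing end date. Either could bring an occasional later sample into Week 8.
- Chemistry is drawn at visits, so the day shares are not detection probabilities, and 30 of the 85 days follow the last dose. On treatment, the column holds one of three scheduled samples.

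**Conclusion.** The concern holds. As written, the Week 8 column cannot count a subject whose recorded end of treatment is before Day 43, nor, apart from the imputation cases above, one whose joint elevation first appears after the last dose. For a subject treated to Day 55 it covers 13 of 85 days (15%; 10–20% for Day 50 to Day 60) and one of four scheduled post-baseline chemistry samples. These figures assume that recorded end dates follow the visit schedule. They describe coverage, not missed cases: the documents give neither a rate nor an onset distribution for joint elevation, so the number uncounted is unknown and may be zero. The change should be made, because this is the only planned by-arm joint count and it is narrower than the tables beside it for no stated reason. It does not touch the efficacy analysis or the type I error.

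**What to change.** In SAP 10.9.4.1, and in the title of CHE_ALT_BIL in SAP 13.11:

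- Count subjects who meet the joint criterion at any post-baseline assessment up to double-blind treatment end plus 30 days. Include unscheduled, premature EOT, Week 10 and post-stop monitoring samples.
- State whether both elevations must be in the same sample and, if not, the interval allowed between them.
- State the denominator.
- Keep the baseline column for reference.

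Optionally, add a row for ALT or AST. The table uses ALT alone with strict inequalities, whereas Protocol 5.1.12 refers to aminotransferases at or above the thresholds. The two should be reconciled, or the difference stated as intended.

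The cost is one table specification. The data are already collected and transferred, and the window is already defined in SAP 5.6.8.1.
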